8.5 Responsibilities of the researcher

It is the responsibility of the Investigator to verify AEs through questioning, pertinent physical examination, assessment of evolution, as well as appropriate medical and pharmacological management; as well as to follow up until the resolution or outcome and definitive discharge of the AE, following the definitions determined in national and international regulations. [33] [47] [48]

In the event of an AE or any event that puts the health and well-being of the subjects at risk, pertinent medical care will be provided, either at the research center or will be referred to the Hospital Center with the highest resolution power with which the research center has a medical care agreement. The PI will notify the sponsor's clinical monitor, according to the times established in national and international regulations. In the case of serious adverse events, it will notify the sponsor and record the corresponding information in the eCRF and in turn, inform the IRB and IC.

The attention of the AEs will be carried out according to the event care diagram (see Figure 3. Adverse Event Care).

The sponsor's final report will include the report of adverse events in compliance with current national and international regulations. [33] [47]

If the research subject debuts during their participation in the study with any chronic adverse event, such as diabetes or systemic arterial hypertension, they will be referred to the competent health professional for chronic treatment. The follow-up and termination of their participation will be in accordance with the stipulations of NOM-012-SSA3-2012. [33]

8.5.1 Recording of adverse events in the electronic case report form

The adverse event registry considers:

- Subject identification information such as: subject number, age, gender, and if applicable specify the eye.
- Information about the causality of the adverse event, its relationship to investigational products, or to another drug related to the study, as appropriate.
- Important date information:
 - Date on which the adverse event occurs.
 - Date on which the Principal Investigator becomes aware of it.
 - Date of resolution or outcome, as applicable.
- Information on diagnosis and clinical management.
- Record the outcome or resolution of the event:
 - Recovered/resolved
 - Recovered/resolved with sequelae
 - Recovering/Resolving
 - Not Recovered/Unresolved
 - Subject who presented death due to the adverse event
 - Subject who presented death and it is judged that the research product may have contributed
 - Subject who presented death and this is not related to the product under investigation
 - Unknown
- Information about the investigational product or product associated with the Adverse Event, Incident, Adverse Incident, AMR or SRAM must be recorded. The information essential for registration is the generic name, distinctive name or code of the investigational product or of the product associated with the undesirable clinical manifestation; it will also be necessary to enter the data concerning the batch number, manufacturing laboratory, expiration date, dose, route of administration, start and end dates of administration and/or consumption, reason for

prescription; according to whether it is an investigational product or drug (protocol in which the subject currently participates) or whether it is a drug that the research subject consumes for the treatment of underlying concomitant diseases or uses for the management of some transitory sign or symptom that does not correspond to the Natural History of the pathology that motivated its entry into the research protocol.

- Indicate whether the removal of the suspected product (of causing the event) eliminates the adverse event. Also indicate if a dose adjustment is made, if the event changes in terms of intensity or seriousness, persistence of the reaction. It is important to indicate whether in those subjects who are exposed again to the product, which had previously been suspended, the AD reappears.
- Information regarding concomitant pharmacotherapy. Indicate the generic name, the dose, the route of administration, start and end dates of its use, as well as the reason for the prescription, regardless of whether it is in accordance with the prescribing information or technical data sheet or is used outside the regulations or what has been authorized by the local, national or international regulatory authority.
- Relevant medical history information. The analysis of the AE considers the information previously narrated, despite the clinical context in which this harmful phenomenon occurs in the participants of the clinical research protocol, is of special interest, so the information about previous conditions, hypersensitivity or allergy phenomena, previous surgical procedures, laboratory analyses or cabinet examinations that have been performed on the participant, etc., that the researcher deems it appropriate to mention may do so.

8.5.2 Adverse Event Tracking

The Principal Investigator will provide care and follow-up of the adverse event presented by the participant until its outcome, according to what is referred to in the following section.

8.5.2.1 *Diagnosis against signs or symptoms*

Whenever possible, an AE should be assessed/reported as a diagnosis and not as a sign or symptom (e.g., liver failure or hepatitis rather than jaundice, asterixis, and elevated transaminases). If a diagnosis cannot be made from the signs or symptoms, then each sign or symptom should be recorded as an AE. If a diagnosis is made later, all AEs reported as signs or symptoms should be nullified and replaced by a single adverse event based on the diagnosis, with an onset date that corresponds to the onset date of the first symptom or sign of the eventual diagnosis.

8.5.2.2 *Adverse events secondary to other adverse events*

In general, AEs secondary to other AEs (cascading events or sequelae) should be identified according to the primary cause, with the exception of serious events. A medically important AE secondary to an AE that is separated in time from the initial event should be reported as a separate event in the EA section of the eCRF. For example:

If vomiting results in mild dehydration without additional treatment in a normal adult, vomiting should only be reported on the eCRF.

If vomiting results in severe dehydration, both events should be reported separately on the eCRF.

If severe gastrointestinal bleeding leads to renal failure, both events should be reported separately on the eCRF.

If a dizziness event leads to a fall and subsequent fracture, then all three events should be reported separately in the eCRF.

If neutropenia is accompanied by infection, both events should be captured independently in the eCRF.

All EAs must register separately if there are concerns regarding the association of events.

8.5.2.3 Persistent or recurrent adverse events

A persistent adverse event is one that spreads continuously without resolution between different points of assessment of the subject. Such events only need to be registered once in the eCRF. The initial severity (intensity or degree) of the event will be recorded at the time of the first AD record. If a persistent AE becomes acute, the maximum severity should be recorded in the appropriate section of the eCRF. If the event becomes a serious event, it must be reported no later than 24 hours after the knowledge of the change in the status of the event. The eCRF section should be updated to reflect the serious status, and will record the date on which the event became serious, thus completing all relevant serious EA reporting data.

A recurrent AE is one that resolves between assessment points and subsequently reappears. Each recurrence of the EA must be recorded separately in the eCRF.

8.5.2.4 Abnormal vital signs

Not all abnormal vital signs qualify as AS. For an abnormal vital sign to be reported as an AD, it must meet any of the following criteria:

- Be accompanied by clinical symptoms. It results in a change in treatment (dose modification, treatment interruption, etc.).
- The report of abnormal values should focus on obtaining a diagnosis and not just a description of the abnormality.

8.5.2.5 Death

Death should be considered an outcome and not an event. The event or condition that caused or contributed to the fatal outcome should be recorded as the EA in the eCRF section.

8.5.2.6 Pre-existing medical conditions

A pre-existing medical condition should be recorded as AE only if the frequency, severity, or characteristics of the condition worsen during the study.

8.5.2.7 Hospitalization or prolonged hospitalization

Any AE that results in hospitalization or prolongation of hospitalization must be documented or reported as a serious AE with the following exceptions:

Hospitalization for pre-existing conditions as long as the following are met:

Hospitalization was planned before the study.

8.5.2.8 Pregnancies, miscarriages, and birth defects

Fertile women should contact their doctor to report any suspected pregnancy during the study. A pregnancy report must be issued and the sponsor must be informed immediately. Monitoring of the subject should continue until the outcome of pregnancy. Pregnancy is not by itself an AE.

Any abortion should be classified as a serious AE.

Any birth defect or birth defect in a product from a woman who received the study drug should be classified as a serious AE.

8.5.3 Procedures for a serious adverse event

The process of attention to the adverse event considers the following stages:

[figure not shown]

Figure 3. Adverse Event Care

During the development and conduct of this study, undesirable harmful events or adverse reactions/incidents, of medical implication, may occur in the research subject, which do not necessarily have a causal relationship with the investigational products. These harmful phenomena can occur during the use of investigational pharmaceutical products at doses authorized for use in humans by a local, national or international regulatory authority. However, it may be suspected that the investigational product causes some unwanted clinical manifestation. AEs, Incidents, Adverse Incidents, ADRs or SRAMs to one or more pharmaceutical products can occur during the systematic evaluation of the participants (on the days when the clinical review is scheduled, according to the schedule of activities) or suddenly, in such a way that:

1. The investigator must be the first person to whom the subject notifies that he or she has developed or presented any harmful phenomenon of a clinical nature during his or her participation in this study.
2. According to his clinical judgment; Based on the pertinent physical examination, interrogation, etc., as well as the analysis of the information available in the medical literature and what is referred to in the Investigator's Manual, Information to prescribe

or Summary of the Comparator Drug, the principal investigator determines the pertinent care of the harmful event/reaction.

3. Such care can be in the research center or in the hospital with the greatest resolution power. In such a way that, in the event that the subject is sent by the PI to a hospital, he or she attends through a referral system. The reference can be with a card that identifies the subject as a study participant and links him or her to the pre-established agreement with the institution, or through a medical reference note issued by the Principal Investigator. Laboratorios Sophia, S.A. de C.V., will pay the expenses for the medical care of the participating subject, when the adverse event is associated with or related to the product under investigation.

4. Taking the clinical information collected, either during the care provided at the research center or that provided by the treating physician(s) in the hospital, the PI will record the AE in its clinical note, stating the seriousness, intensity (mild, moderate or severe) and relationship with the investigational product.

5. The PI must migrate the relevant data to the eCRF and its respective adverse event section. By virtue of the fact that, in cases of serious adverse events, the clinical monitor of the study must be notified within 24 hours after learning of it, so that in turn it informs the Clinical Team and the Pharmacovigilance and Technovigilance Unit of Sophia Laboratories (UFTLS), and that the CEI/CI is subsequently notified. Non-serious adverse events will be recorded and treated appropriately and the safety profile of the investigational drug or drug will be reported to the appropriate regulatory authority in the final report of the clinical trial.

The recording of the outcome of the AE depends substantially on the follow-up that the Principal Investigator performs on the subject, since it is expected that most of the harmful phenomena (see subsection 2.5 Risk-benefit assessment and consult the Investigator's Manual) are ophthalmic in nature, however, there may be systemic alterations. Therefore, in the opinion of the researcher, the withdrawal of the participant or their permanence will be considered.

8.5.4 Causation assessment

Causality assessment is the methodology used to estimate the probability of attributing the observed adverse event to a pharmaceutical product. It considers probabilistic categories according to the available evidence and the quality of the information, based on the national pharmacovigilance and technovigilance regulations, the World Health Organization and the Uppsala Monitoring Center. [33][51]

An adverse event may or may not be related to the clinical trial. A causal relationship means that the intervention caused (or is reasonably likely to have caused) the adverse event. This usually implies a relationship between the time of the intervention and the adverse event (e.g., the adverse event occurred shortly after the subject under investigation received the intervention). [49]

For all adverse events, the Principal Investigator is responsible for examining and evaluating the subject to determine the association of the event with the clinical study and the intervention, whether related to the experimental treatment, concomitant, surgical procedure, or diagnostic procedures performed during the study. [49]

Accepting that the adverse event is related to the clinical study requires a plausible mechanism of action, that is, that there is a logical sequence between the event that occurred and the intervention that caused it. In some cases, it is helpful to know the opinion of other doctors directly or indirectly involved in the research; as well as whether the subject considers that a relationship exists or not. [49]

UFTLS may employ the causation categories described by *the Uppsala Monitoring Centre*, to categorize the likelihood of adverse event to the investigational product or concomitant treatments or treatments used during visits: [33] [51]

- Definitive (certain): a clinical event, including alterations in laboratory tests, that manifests itself with a plausible temporal sequence in relation to the administration of the drug, and that cannot be explained by concurrent disease, or by other drugs or substances. The response to drug withdrawal (withdrawal) must be clinically plausible. The event must be definitive from a pharmacological or phenomenological point of view, using, if necessary, a conclusive re-exposure (challenge) procedure. [33] [51]
- Probable: A clinical event, including alterations in laboratory tests, that manifests itself with a reasonable time sequence in relation to the administration of the drug, that is unlikely to be attributed to concurrent disease, or to other drugs or substances, and that a clinically reasonable response is presented upon withdrawal. It is not necessary to have re-exposure (challenge) information to assign this definition [33] [51]
- Possible: A clinical event, including alterations in laboratory tests, that manifests itself with a reasonable time sequence in relation to the administration of the medicinal product, but which can also be explained by concurrent disease, or by other drugs or substances. Information regarding the withdrawal of the drug may be missing or unclear. [33] [51]
- Unlikely: A clinical event, including alterations in laboratory tests, that manifests itself with an unlikely temporal sequence in relation to the administration of the drug, and that can be more plausibly explained by concurrent disease, or by other drugs or substances. [33] [51]
- Conditional/Unclassified: A clinical event, including alterations in laboratory tests, reported as an adverse reaction, for which further data are essential for appropriate evaluation, or additional data are under review. [33] [51]
- Non-assessable/Unclassifiable: A notification that suggests an adverse reaction, but cannot be judged because the information is insufficient or contradictory, and that cannot be verified or completed in its data. [33] [51]

Thus, the degree of certainty to establish the investigational product as the causal agent of the harmful phenomenon that occurs to the subject of the clinical study, can be indicated directly by the Principal Investigator based on his clinical experience or by applying the categories of causality described by *the Uppsala Monitoring Centre*. It is important that the researcher and the UFTLS take into account the following arguments in favor of the causal relationship:

- a) Strength of association, which refers to the number of cases in relation to those exposed.
- b) The consistency of the data, i.e. the presence of a common characteristic or pattern.
- c) The exposure-effect pattern, which determines the relationship with the site of appearance, time, dose and reversibility after deletion.
- d) Biological plausibility, which refers to the possible pharmacological or pathophysiological mechanisms involved in the development or presentation of the adverse event.
- e) Experimental findings, e.g., the appearance of abnormal metabolites or high levels of the drug or its biotransformation product.
- f) Analogy, which refers to the experience gained with other related drugs, adverse reactions frequently produced by the same family of pharmacological agents.
- g) Nature and characteristics of the data, i.e. objectivity, accuracy and validity of the relevant documentation. [52]

9. Study Monitoring

The study sponsor is responsible for monitoring the study. Monitoring activities include, but are not limited to: general safety monitoring, general study quality monitoring, monitoring by study site, detection monitoring, reporting and tracking of adverse events, monitoring for resolution of discrepancies in data capture, etc.

Responsibility for monitoring activities and ultimate responsibility for monitoring rests with the sponsor.

The details of the monitoring activities are specified in a separate document from this protocol in a Monitoring Plan.

9.1 Monitoring the Study Site

The research center participating in the study will be monitored. For each centre, at least one start visit and one closing visit must be carried out, which does not exclude the carrying out of one or more follow-up visits between these two mandatory visits.

The initial visit must be carried out before the inclusion of the first participant in that center; In it, the monitor will verify that the material to be used during the study has been received and that the personnel who will participate in the study activities have been trained on the study, as well as verify that the regulatory requirements and applicable standard operating procedures are met.

At the follow-up visit(s), the monitor will conduct a review of the study documents to confirm that the applicable research protocol and standard operating procedures are being followed, data completion is complete and timely, and that adverse event reports are being conducted appropriately. At each visit, the monitor will discuss the findings with the researcher and define the actions to be taken.

The closure visit will take place at the end of the study, once the last site participant has been discharged from follow-up. On this visit the monitor will verify that the site has all the necessary documents for archiving, that all biological samples have been analyzed, that all IP (used and unused) has been returned to the sponsor, and that all unused material has been recovered.

Details on monitoring are set out in the corresponding plan.

9.2 Audit and quality assurance

To ensure compliance with Good Clinical Practice (GCP) and all applicable regulatory requirements, Laboratorios Sophia, S.A. de C.V. may conduct quality assurance audits. Regulatory agencies could also conduct a regulatory inspection of this study.

Details about the audit process are set out separately in the Audit Plan.

They may take place at any time before, during, or after the conclusion of the study. If any audit or inspection is conducted, the investigator and the institution shall agree to allow the auditor/inspector direct access to all relevant documents, and shall allocate their time and that of their staff to the auditor/inspector to discuss the findings and any pertinent problems. In the event that the audit has not been scheduled by the sponsor, the facility must notify Laboratorios Sophia, S.A. de C.V. immediately.

10. Sample size calculation and statistical analysis

10.1 Sample Size Calculation

Bacterial conjunctivitis is commonly self-limiting, resolving after about 10 days, and can rarely last more than 3 weeks. Its most common treatment is the use of antibiotics with a broad spectrum of action on the variety of ocular pathogens. Proper management of bacterial conjunctivitis reduces the time to resolution of the disease, minimizes the risk of sequelae, helps prevent the spread of infection, and decreases the time the patient can spend away from work or school. Moxifloxacin hydrochloride is a fourth-generation fluoroquinolone, its use in topical ophthalmic presentation for the treatment of bacterial conjunctivitis has been approved since 2003 in the United States. Moxifloxacin is one of the most potent fluoroquinolones evaluated for ophthalmic use for bacterial eradication. There is sufficient evidence on the safety and tolerability of moxifloxacin. Commonly reported AEs are eye pain, eye burning/irritation, hyperemia, and tearing; most of them of mild intensity and transient.[53] [54, 55] [54] [53, 55, 56, 57, 58]

Considering this information and the primary objective of the study; To evaluate the safety and tolerability of PRO-231 ophthalmic solution (moxifloxacin 0.5%) on the ocular surface of clinically healthy subjects, the following proposal was made for the sample size.

10.1.1 Calculation methodology

Although sample estimation in phase 1 studies is common in treatments whose toxicity/risk is high, as it is in clinical studies for the management/survival of cancer; It was considered pertinent to estimate the sample size according to the safety profile reported in the literature after the use of moxifloxacin hydrochloride. Considering the primary safety variables of the protocol: [59]

- Incidence of AD
- Changes in ophthalmologic signs
- Changes in the AVMC
- Changes in fluorescein staining of the ocular surface

The equation was used to compare two proportions: two samples, two sides of equality. This calculation is useful when you want to test whether the proportions of two groups are different (Incidence of AD in VIGAMOXI® is different from the incidence of AD in PRO-231). The following formulas are used for the calculation to compute the sample size and power respectively: [60]

$$n_A = kn_B \text{ y } n_B = \left(\frac{p_A(1 - p_A)}{k} \right) \left(\frac{z_{1-\alpha/2} + z_{1-\beta}}{p_A - p_B} \right)^2$$

$$1 - \beta = \Phi\left(z - z_{1-\alpha/2}\right) + \Phi\left(-z - z_{1-\alpha/2}\right), z = \frac{p_A - p_B}{\sqrt{\frac{p_A(1-p_A)}{n_A} + \frac{p_B(1-p_B)}{n_B}}}$$

Where:

$k = n_A/n_B$: ratio between the sample sizes of the two groups

Φ : Function of Standard Normal Distribution

Φ^{-1} : The standard normal quantile function

α : error tipo I

β : error tipo II

The proportion of subjects who had at least one AE (ocular and non-ocular) was considered in the study by Garg et al. (2015), where they evaluated the clinical and antibacterial efficacy, as well as the safety of besifloxacin ophthalmic suspension compared to moxifloxacin 0.5% (besifloxacin; n=61, moxifloxacin; n=62). A total of 6 ocular AEs were present in subjects treated with moxifloxacin and at least one AE occurred in 3 patients. The most common AE was conjunctivitis (3.2%). For the expected proportion of subjects of PRO-231, 50% was used, which is a conservative value and gives larger samples. The calculation was made using the free software R (R Core Team, 2021), using a code available online for this purpose. [56] [61] [62]

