7.4 Outcome variables

7.4.1 Primary outcome variables

7.4.1.1 Security

- Incidence of unexpected AEs related to interventions.
- Incidence of conjunctival hyperemia and chemosis.
- Changes in the AVMC evaluated with the Snellen chart.
- Changes in ocular surface integrity using fluorescein staining, using the Oxford scale.

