10.1.2 Size Calculation

PRO-231 ophthalmic solution is expected to be safe in its ophthalmic application as it presents an incidence of AE similar to that presented by VIGAMOXI.®

On this basis, a sample of 17 ophthalmologically and clinically healthy subjects was estimated. This value increased by 10% considering possible losses. Based on this consideration, 19 subjects per arm (38 subjects in total) are required to provide one eye (OD) to respond to the primary objective of the study.

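### The sample size is derived for subjects with any AE, not for unexpected related AEs or any other primary variable, and it rests on an assumed 50% AE rate for PRO-231

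*Combined protocol and SAP*

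**What the plan says.** **Sizing.** Section 10.1.1 names four primary safety variables as the basis for the calculation, the first being the incidence of AD (evidently AE), and then uses a single input: "The proportion of subjects who had at least one AE (ocular and non-ocular) was considered". There is no restriction by relatedness or expectedness. The comparator rate comes from a published study with 62 moxifloxacin patients: "A total of 6 ocular AEs were present in subjects treated with moxifloxacin", and "at least one AE occurred in 3 patients". For the test product, "For the expected proportion of subjects of PRO-231, 50% was used, which is a conservative value and gives larger samples".

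**Result.** Section 10.1.2 expects PRO-231 to have an AE incidence similar to VIGAMOXI. It reports 17 subjects, adds 10% for losses, and concludes that 19 per arm (38 in total) "are required to provide one eye (OD) to respond to the primary objective of the study".

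**Primary variables.** The AE variable in 7.4.1.1 is "Incidence of unexpected AEs related to interventions"; the synopsis and 3.1.2.1 agree. The others are conjunctival hyperemia and chemosis, best-corrected visual acuity, Oxford staining and, in 7.4.1.2, the eye comfort score. The comfort score does not appear in 10.1.

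**Other AE variables.** Section 7.4.2.1 makes expected, related AEs secondary. The footnote to Table 5 describes the secondary AE row as covering AEs whether or not related to the product.

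**The concern.** The AE variable in the calculation is not the AE variable in the outcome list. Unexpected related AEs can be no more frequent than AEs of any kind, and probably much rarer. Section 7.4.4.6 lists burning, foreign body sensation, pruritus, hyperemia and chemosis among the events that can occur with PRO-231, and 7.4.4.3 does not count burning, foreign body sensation, pruritus or tearing as AEs. What is left for an unexpected related AE is small.

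What is at stake is how a null result will be read. The decision table in 10.3.1 treats p of 0.05 or more, with an interval that includes zero, as acceptance of H0 and as showing that the treatments are similar. If 38 subjects are said to be sufficient for the primary objective, a non-significant comparison of unexpected related AEs will look like a finding, although the trial could hardly have produced anything else.

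**Working it through.** **Inputs from the documents.** Comparator 3/62 = 4.8% (subjects with an AE) or 6/62 = 9.7% (if the six events were counted as subjects); PRO-231 50%; two-sided comparison of two proportions (10.1.1); alpha 0.05 (10.3.1); 1:1 allocation (7.3); losses 10% (10.1.2). No power is stated, so I take 80% to 95%.

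**1. Reproducing 17.** The printed sample-size formula contains the variance of one arm only. With 3/62 it gives 2 to 3 per arm if VIGAMOXI is group A and 10 to 16 if PRO-231 is, so not 17 at these powers. The printed power formula carries both variances, and I use the matching form:

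n = [pA(1−pA) + pB(1−pB)] × [(z0.975 + z_power)/(pA − pB)]²

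- 3/62 v 50%, 80% power: (0.0460 + 0.25) × 7.849 / 0.2040 = 11.39, so 12. At 85%, 90% and 95% power: 14, 16 and 19.
- 6/62 v 50%, 80% power: (0.0874 + 0.25) × 7.849 / 0.1626 = 16.29, so 17.

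The second line matches, but it does not prove which input was used. For example, the 3.2% quoted for the commonest AE gives 16.67, also 17, at 95% power. The losses step is sound: 17 × 1.1 = 18.7 and 17/0.9 = 18.9, both rounded up to 19.

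**2. What 17 and 19 per arm can detect.** Exact two-sided Fisher power, by enumeration:

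| Rates | 17 per arm | 19 per arm | Source of rates |
|---|---|---|---|
| 3/62 v 50% | 82% | 88% | section 10.1.1 |
| 6/62 v 50% | 64% | 72% | 10.1.1, events as subjects |
| 1% v 50% | 95% | 97% | 1% assumed |
| 5% v 20% | 12% | 15% | assumed |
| 2% v 10% | 1.6% | 2.4% | assumed |

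The documents give no rate for unexpected related AEs, so the last two rows are illustrations. With no events in one arm, significance needs five in the other: 0 v 5 gives p = 0.044 at 17 per arm (0.046 at 19), and 0 v 4 gives about 0.10 at either size.

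**3. Is 50% conservative?** It maximises the variance of a single proportion. In a comparison with a rate near 5% it mainly enlarges the difference to be found, and so shrinks the sample. For 80% power by the same formula, 4.8% v 20% needs 71 per arm, 4.8% v 15% needs 132, and 4.8% v 10% needs 401.

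**4. Precision for the primary AE variable.** With no events in n subjects, the two-sided 95% upper limit is 1 − 0.025^(1/n): 19.5% for 0/17 and 17.6% for 0/19.

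**The case against.** The best defence is that any AE is a reasonable umbrella for the safety objective. Section 10.1.1 itself calls AE incidence a primary safety variable. Any AE contains the unexpected related AEs and also takes in the AE thresholds of the other primary signs: hyperemia of grade 3 or more, any chemosis, loss of two or more lines, and Oxford grade III or more (7.4.4.1, 7.4.4.2, 7.4.4.4, 7.4.4.5). Section 10.1.2 refers to the primary objective as a whole and does not name unexpected related AEs. All of that is true. It makes any AE a related quantity, but not the variable that 7.4.1.1 defines, and 10.1.1 and 7.4.1.1 still disagree.

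A second defence is that phase I safety trials need no formal power. This plan nevertheless chose a hypothesis test, a two-proportion calculation and a decision table, so its size claim has to match them.

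Three stronger readings are tempting and are not supported:

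- *That the narrower variable is what destroys the power.* With 50% held for PRO-231, a rarer comparator event raises power (95% for 1% v 50%, against 82% for 3/62 v 50%). The 5% v 20% row is close to the comparator's own any-AE rate, so the weakness applies to any AE as well. Its main cause is the 50% assumption.
- *That the size is adequate for any AE.* It is adequate only for a rise to about 50%, and perhaps not then, if 6/62 was the input.
- *That the planning rate comes from infected patients.* The study is described as measuring antibacterial efficacy, but its patients' diagnosis is not given.

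**Conclusion.** The point stands as an inconsistency between endpoint and sizing; the step from 17 to 38 is arithmetically correct. Section 10.1 derives 17 per arm for subjects with any AE under an assumed 50% for PRO-231. It gives neither size nor precision for unexpected related AEs or for any other primary variable, so the statement in 10.1.2 that 38 subjects are required for the primary objective is unsupported.

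The 50% figure conflicts with the similar incidence expected in 10.1.2 and is implausible for either AE variable. Power falls from 82% (or 64%) under the plan's assumption to 12% for 5% v 20% and 2% for 2% v 10%. The exact percentages in the last two cases depend on assumed rates. Two results do not: the five-to-none split needed for significance, and the upper limit of 19.5% after 0/17.

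Sections 3.2 and 10.3.1 do warn about absence of evidence, but the decision table reads a non-significant p together with an interval that includes zero as similarity. That reading is not safe for this variable.

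**What to change.** No change in the number of subjects or visits is needed.

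- **Section 10.1.2:** state that 17 per arm was derived for subjects with at least one AE of any kind, with PRO-231 assumed at 50%; that it detects only a rise to about that level; and that the trial is not powered for unexpected related AEs. Give the comparator count used (3/62 or 6/62) and the power. Remove the claim that 50% is conservative. Do not describe any AE as a variable that the size adequately supports.
- **Precision:** for unexpected related AEs, give the two-sided 95% upper limit after no events: 19.5% for 0/17 and 17.6% for 0/19.
- **Section 10.3.1:** say that a non-significant result on this variable is not evidence of similarity.
- **Tables:** tabulate by arm the subjects with at least one AE of any kind. Sections 7.4.4.6 and 8.3 already require the data. Reconcile the Table 5 footnote (related or not) with 7.4.2.1 (expected and related).

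The cost is some rewording and one extra table. The sizing claim becomes less favourable to the sponsor.
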